MAGIPAC trial: Magnetic Resonance Imaging for Better Selection of Pancreatic Cancer Patients for Surgery: A Randomized Clinical Trial.

BACKGROUND AND SIGNIFICANCE

Pancreatic cancer has a dismal prognosis with a 5-year survival of only 8% [1]. Despite surgery being the only chance for cure, only 20% of the patients are eligible for surgical treatment, as most have metastatic disease at diagnosis [2]. Pancreatic cancer surgery is a major procedure with a substantial morbidity and mortality [3]. Therefore, it is important to avoid futile resections that will delay initiation of life-prolonging chemotherapy in patients who will not benefit from surgery. Whether the patient can be operated depends on the local extent of the tumor and the presence of distant metastases (most often in the liver), which are contraindications to surgery [4-6].

Currently, computed tomography (CT) is state-of-the-art for assessing pancreatic cancer resectability [7]. However, CT has some shortcomings. Although it performs well in assessing the local extent of the tumor, it has limited sensitivity for detecting small liver metastases in pancreatic cancer [8]. Relying solely on CT imaging therefore leads to futile resections in patients with undetected liver metastases. This will impair survival, as patients will have to recover from surgery and the associated complications before they can initiate chemotherapy. These shortcomings may be overcome by using liver and pancreatic magnetic resonance imaging (MRI) instead of CT.

MRI may be superior to CT for detection of liver metastases in pancreatic cancer [9]. As liver metastases from resectable pancreatic cancer tend to be small [10], for which MRI (with use of diffusion weighted imaging and liver-specific contrast) has a high sensitivity, routine use of preoperative MRI could be beneficial. However, the feasibility of using MRI in detection of liver metastases in pancreatic cancer patients has been sparsely investigated. One prospective study of 69 pancreatic cancer patients found that almost 25% had liver metastases on MRI that were not visible on CT [11], whereas a retrospective study of 216 patients found that MRI revealed liver metastases in only 5% of patients with CT-assessed non-metastatic pancreatic cancer [12]. The latter study also found a longer time to recurrence after surgery in patients undergoing preoperative MRI, suggesting that preoperative MRI may be beneficial in pancreatic cancer patients. However, they did not provide information on why MRI was performed, and findings are unlikely to be generalizable. Furthermore, only few studies have examined the use of MRI in assessing the local extent of the tumor, suggesting it is not inferior to CT [13, 14].

Thus, MRI may provide a superior alternative to conventional CT in order to improve treatment allocation for pancreatic cancer patients. However, there is a substantial need for high-

quality research to examine this. Specifically, no randomized clinical trial (RCT) has been conducted.

PURPOSE AND OVERALL AIM

[figure not shown]
We propose to conduct a nationwide RCT to examine the feasibility of using MRI for tumor staging and identification of liver metastases in pancreatic cancer patients. *The aim is to improve selection of pancreatic cancer patients for surgery in order to increase overall survival*. Within this RCT, we will conduct three studies outlined below.

STUDY POPULATION AND DESIGN

Patients

200 patients with CT-assessed resectable pancreatic cancer allocated to surgery by the local multidisciplinary tumor board (MDT) will be included. Patients will be randomized to either the intervention (preoperative MRI, n=100) or control/standard-of-care (no preoperative MRI, n=100) arm.

Study design and patient flow

An overview of the proposed study design is shown in Figure 1.

Upon consent, patients will be electronically randomized to one of the two treatment arms. Patients in the control arm will proceed directly to surgery. Patients in the intervention arm will have an MRI performed after randomization and before treatment. If the interval from CT to MRI is >14 days, a new CT will be performed to assure a valid comparator. The MRI will be read by an experienced gastro-radiologists blinded to the patient's identity and initial CT scan. Based on the MRI, the treatment decision will be made (*Figure 2*):

Figure 1. Study design. R: Randomization.

- 1) No liver metastases on MRI (expected ~75%): Surgery as planned.
- 2) Non-specific liver lesions on MRI, not seen on CT (expected $\sim 10\%$): Surgery as planned.
- 3) Liver metastases on MRI (expected ~15%): Referral to liver biopsy and oncological treatment if malignancy is verified. If biopsy is inconclusive, repeat liver MRI after one month.

[figure not shown]

Figure 2. Patient flow in the intervention arm. MDT: Multidisciplinary team conference.

Follow-up

Patients will be followed for up to three years for information on treatment, recurrence, and vital status. We will conduct standard-of-care follow-up CT at 3, 6, 9, 12, 18, 24, 30, and 36 months postoperatively in all patients. Primary end-point for this project will be one-year survival. For subsequent studies, we will also perform analyses of three-year survival.

SPECIFIC STUDY AIMS, HYPOTHESES AND OUTCOMES

Study I: To compare tumor staging of pancreatic cancer patients assessed by MRI versus upper abdominal CT.

Study II: To assess the ability of MRI to detect liver metastases in pancreatic cancer patients with resectable tumor on CT.

Study III: To assess the impact of MRI on treatment allocation, recurrence, and survival in pancreatic cancer patients with a resectable tumor on CT.

Details of study hypotheses, population, and analytical plans are outlined in Figure 3.

	Study I	Study II	Study III
Aim	To compare tumor	To assess the ability of	To assess the impact of
	staging of pancreatic	MRI to detect liver	MRI on treatment
	cancer patients assessed	metastases in pancreatic	allocation, recurrence,
	by MRI versus upper	cancer patients with	and survival in pancreatic
	abdominal CT	resectable tumor on CT	cancer patients with a
			resectable tumor on CT
Hypothesis	MRI is non-inferior to CT	MRI will detect liver	Use of MRI will change
	with respect to tumor	metastases in patients	treatment allocation and
	staging	with a resectable tumor	improve overall survival
		on CT	
Population	Patients in the	Patients in the	Patients in both arms
	intervention arm (N=100)	intervention arm (N=100)	(N=200)
Analysis	Agreement assessed by	Agreement assessed by	Treatment allocation and
	intraclass correlation	intraclass correlation	recurrence by Chi ² test
	coefficient (ICC)	coefficient (ICC)	Survival analyses by
			Kaplan-Meier estimation

Figure 3. Outline of the three studies.

POWER CALCULATIONS AND FEASIBILITY

Assuming alpha=0.05, power of 80%, and a hazard ratio of death of 1.5, we need 191 patients in total. To guard against dropout of 5%, we aim to include 200 patients. On average, all four institutions performing pancreatic cancer surgery in Denmark (Rigshospitalet, Aarhus, Aalborg, and Odense) shall include 50 patients. We aim to finalize patient enrollment during the first 18 months of the study period, equaling to 2.8 patients monthly in each institution. In total, ~300 resections will be performed during this 18-month period. We consider it feasible and realistic to include two-thirds of these patients.

IMAGING PROTOCOLS

CT imaging protocol

As a part of the routinely workup for staging pancreatic cancer, all patients referred to the local hepato-pancreato-biliary MDT board undergo a pancreas-specific CT scan. All CT scans include a

portal venous phase (PVP) of the liver. CT scanners from different vendors will be used to acquire the images. The PVP will routinely obtained by 120 KV and mAs range from 150 to 290 depending of the body mass of the patient and the scan system. Contrast medium will be administered intravenously as a bolus injection by weight bases contrast Iodine concentration of 500 – 750 mg I/kg and a rate of 3-5 ml/s, followed by a saline flush of 20–40 ml. The scan delay for the PVP will be 50 sec (post-threshold, bolus tracking). Axial slice thickness of 2 mm slices will be reconstructed with 1 mm increments.

MR imaging protocol

The MRI will be performed using 1.5 or 3.0 T MR scanners of different vendors. The liver will be scanned using axial and coronal T2W single shot (SS) TSE, axial DWI (minimum b-values of 50 and 800) and axial T1W 3D spoiled gradient echo for gadoxetic acid (Primovist, Bayer Pharma, Berlin, Germany) contrast scans. Both a dynamic contrast scan consisted of; pre-contrast phase, arterial phase (timed using bolus tracking) followed immediately by porto-venous phase; late phase at 2 min and hepato-biliary phase 15 min after contrast injection. The gadoxetic acid contrast will be injected at 1 or 2 mL/s depending of using a dilution 1:1 of gadoxetic acid and saline 9mg/ml or not. The dose will be 0.025 mmol/kg body weight with a maximum of 2.5 mmol using a power injector.

Analysis for metastatic lesions

Each modality will be read anonymized. Both CT and MRI images will be read independently by dedicated radiologist from each participating site as part of the routine work-up in staging pancreatic cancer. The CT scan will be performed as the first examination followed by MRI scan within 14 days after the CT scanning. For all focal hepatic lesions confidence of malignancy will be categorized via a 3-point scale, 1: benign, 2: indeterminate, 3: malignant.

FEASIBILITY

Time schedule

The project will begin in January 2022 and end in December 2024. We will include the patients within the first 18 months of the project period. In the final year of the study period, we will perform data analyses and writing of scientific papers. This will allow for a sufficient follow-up period of all patients (please see *Figure 4* for detailed time schedule).

[figure not shown]

Figure 4. Time schedule.

Scientific and non-scientific personnel

At each institution, one research nurse will be responsible for identification of potential study subjects and, in collaboration with the surgeon, perform the practical work on obtaining informed consent and randomize the patients. The research nurse will also be responsible for each patient's path through the project, *e.g.* schedule the imaging and collect data, and to coordinate the project with the research nurses at the other participating sites.

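### Study II sets out to assess MRI's ability to detect liver metastases, but the roughly 85% of the arm sent to surgery have no liver reference, so sensitivity and negative predictive value cannot be estimated

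*Combined protocol and SAP*

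**What the plan says.** The section on specific study aims gives the aim of Study II as "To assess the ability of MRI to detect liver metastases in pancreatic cancer patients with resectable tumor on CT". Figure 3 (the outline of the three studies) restricts it to the intervention arm, N=100, and gives one analysis: "Agreement assessed by" the intraclass correlation coefficient. It names no reference standard and does not define a false negative.

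The section on study design and patient flow sorts the MRI results into three groups:

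- Negative: "No liver metastases on MRI (expected ~75%): Surgery as planned".
- "Non-specific liver lesions on MRI, not seen on CT": about 10%, also to surgery.
- Metastases on MRI: about 15%. "Referral to liver biopsy and oncological treatment if malignancy is verified". An inconclusive biopsy leads to a repeat liver MRI after one month.

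The Follow-up section adds: "We will conduct standard-of-care follow-up CT at 3, 6, 9, 12, 18, 24, 30, and 36 months postoperatively in all patients". It lists treatment, recurrence and vital status as the information to be collected. Figure 3 uses recurrence only in Study III, by chi-square test in both arms.

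**The concern.** An ability to detect has two sides: how many metastases the scan finds and how many it misses. The patient flow provides a check on the first side only. Patients whose MRI is negative or non-specific go to surgery, and Study II does not look back at whether their livers were in fact clear.

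The agreement analysis does not fill the gap. All patients enter with disease that is resectable on CT, and the Background says CT has limited sensitivity for small liver metastases. If CT is the comparator, agreement cannot count lesions that both scans miss. Study III would record some of these cases as recurrence, but does not relate them to the baseline MRI reading.

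The miss rate is at stake. The Background says that undetected liver metastases lead to futile resections. After an MRI, the patients still at that risk are those operated on with a negative or non-specific result. The Imaging Protocols provide an indeterminate category for lesions, but Study II does not say how such lesions are finally classified.

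**Working it through.** **Inputs from the protocol.** Intervention arm 100 patients; expected MRI results 75% negative, 10% non-specific, 15% positive.

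**Inputs not in the protocol (assumptions).** The share *m* of MRI-non-positive patients with early liver metastases, taken as 5%, 10% or 20%; and the number of MRI-positives confirmed, taken as all 15, or 12 of 15 (80%).

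**Step 1: patients without a liver reference.** 75 + 10 = 85, and 85 + 15 = 100. About 85 of 100 patients have no planned liver verification in Study II; about 15 are referred to biopsy.

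**Step 2: what biopsy of positives can give.** It gives the yield and the proportion of positive calls confirmed. The number missed is not observed. If biopsy were the only reference, the false-negative count would be zero by construction, and apparent sensitivity would be 15/15 = 100% whatever *m* is.

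**Step 3: what the miss rate would do.** Missed = 85 × *m*; sensitivity = confirmed / (confirmed + missed). Non-specific results are counted as negative here.

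| *m* | Missed | Sensitivity, 15 confirmed | Sensitivity, 12 confirmed | Negative predictive value (1 − *m*) |
|---|---|---|---|---|
| 5% | 4.25 | 15/19.25 = 78% | 12/16.25 = 74% | 95% |
| 10% | 8.5 | 15/23.5 = 64% | 12/20.5 = 59% | 90% |
| 20% | 17 | 15/32 = 47% | 12/29 = 41% | 80% |

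**Step 4: precision.** With 15 confirmed and whole patients missed (4, 8 and 17), exact 95% intervals are 54–94% for 15/19, 43–84% for 15/23 and 29–65% for 15/32. The estimate would be imprecise.

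**Step 5: where the later liver information goes.** Follow-up CTs start at 3 months after surgery, but their only stated analytic use is recurrence in Study III. The text sets no link from follow-up CT or operative findings to the Study II reading.

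**The case against.** The best defence is that Study II asks about yield. Its hypothesis is that MRI will detect liver metastases in patients with resectable disease on CT, and the Background frames the gap with two yields, almost 25% and 5%. Sensitivity and negative predictive value are never promised. This stands for the hypothesis, which can be met as planned. It does not cover the wider aim, and the one stated statistic is agreement, not yield.

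Biopsy also appears only as clinical work-up in the patient flow. A reader might infer that it is Study II's formal reference standard and that the trial will report 100% sensitivity. The protocol says neither; the gap is that no reference is named.

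Three further inferences go beyond the text:

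- *The follow-up CTs would reveal the missed metastases.* The protocol itself says CT has limited sensitivity for small liver lesions, and a lesion seen later may be new.
- *A reference that includes follow-up gives a conservative bound on sensitivity.* The errors run both ways. Metastases arising after baseline lower the estimate. Lesions missed by CT or at surgery, and patients who die or drop out before the scan, can raise it.
- *The data are already collected.* The CTs are scheduled, but operative liver findings and site of recurrence are not listed.

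Finally, Study III compares recurrence and survival between randomised arms, so the consequences of missed lesions enter the main comparison. That is true, but it gives no miss rate.

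**Conclusion.** The concern holds in a limited form. As planned, Study II can show yield and the share of MRI-positive calls confirmed, but not sensitivity or negative predictive value, so its stated aim is only partly met. Under the assumptions above, sensitivity anywhere from 78% to 47% (74% to 41% if 12 of 15 are confirmed) would be compatible with the same Study II result. These figures illustrate the size of the gap and do not forecast MRI performance, since the protocol gives neither the miss rate nor the confirmation rate. The primary end-point, one-year survival, is not affected.

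Figure 2 was not available as an image; the written description of the patient flow contains nothing to the contrary.

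**What to change.** In Study II, prespecify a composite liver reference for every intervention-arm patient: a conclusive biopsy where one was done, otherwise liver metastasis found at surgery or on the scheduled 3-month CT. Use the 6-month CT as a sensitivity analysis.

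State in advance:

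- how inconclusive biopsies are classified, because a repeat MRI makes the test under study its own check, and the CT schedule is timed from surgery, so a patient not operated on may have no dated scan;
- how patients without a 3-month CT are classified.

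Report MRI sensitivity and negative predictive value with exact confidence intervals as secondary estimates. Analyse the non-specific group once as negative and once as positive. Label the estimates as approximate, with the errors in both directions described, and not as a conservative bound.

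The cost is analysis wording, some analysis work, and data fields for operative liver findings and site of recurrence. No scan, visit or change in patient management is added. With enrolment over 18 months, the 6-month CTs of the last patients fall at about 18 + 6 = 24 months plus the time to surgery, around the start of the final year set aside for analysis.

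### The stated 80% power belongs to a hazard-ratio comparison with 191 deaths, not to the primary endpoint of one-year survival, for which no between-arm test or data cut-off is named

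*Combined protocol and SAP*

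**What the plan says.** All places are in the combined protocol and SAP.

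- **Follow-up:** "Primary end-point for this project will be one-year survival". The next sentence adds: "For subsequent studies, we will also perform analyses of three-year survival". On data collection: "Patients will be followed for up to three years for information on treatment, recurrence, and vital status". No time origin is given for survival.
- **Power calculations and feasibility:** "Assuming alpha=0.05, power of 80%, and a hazard ratio of death of 1.5, we need 191 patients in total", then "To guard against dropout of 5%, we aim to include 200 patients". No control survival, number of deaths, length of follow-up or sidedness is stated.
- **Figure 3, Study III:** the hypothesis concerns overall survival. Treatment allocation and recurrence are given a chi-squared test, but for survival the only entry is "Kaplan-Meier estimation". No truncation at 12 months is mentioned.
- **Time schedule:** "The project will begin in January 2022 and end in December 2024". Enrolment takes the first 18 months, and analysis and writing fall in the final year. No cut-off date is set.

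**The concern.** The endpoint is survival at a fixed time, while the sizing is for a hazard ratio, whose power depends on the total number of deaths. Nothing links the two. Kaplan-Meier estimation can deliver the one-year proportions, but it is neither a test between arms nor an estimate of a hazard ratio.

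Two things are at stake. First, a reader of the plan will believe that the primary comparison has 80% power; if it has far less, a null one-year result would say little about whether preoperative MRI helps. Second, with the test, effect measure and cut-off all open, a one-year difference, a log-rank test or a Cox model could each be chosen once the data are known.

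**Working it through.** **1. Reproduce the plan's figure.** Schoenfeld's number of deaths for 1:1 allocation is D = 4(z₀.₉₇₅ + z₀.₈₀)² / (ln HR)². With HR 1.5, two-sided 5% and 80% power: D = 4 × (1.960 + 0.842)² / (0.4055)² = 191. The match is exact, and the formula counts deaths. The one-sided version gives 151, so the plan evidently used a two-sided 5% level. Reaching 191 deaths among 200 patients would need about 96% of them to die within the analysis window (191/200 = 0.955).

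**2. Inputs for the expected deaths.**
- From the documents: 100 per arm, HR 1.5, 18 months of accrual from January 2022, project end December 2024.
- Assumed: control one-year survival S from 50% to 80%, exponential survival, constant hazard ratio (control versus MRI arm), uniform accrual, no dropout.

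**3. Formulas.** Monthly control hazard λ = −ln(S)/12; MRI-arm hazard λ/1.5. The probability of death by 12 months is 1 − e^(−12λ). With follow-up uniform between a and b months it is 1 − (e^(−λa) − e^(−λb)) / (λ(b − a)). Power = Φ(½√d × ln 1.5 − 1.96), where d is the total of expected deaths.

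A cut at mid-2024 gives 12-30 months of follow-up and is the earliest that gives every patient 12 months. A cut at the end of December 2024 gives 18-36 months.

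**4. Example, S = 70%.** One-year survival in the MRI arm is 0.70^(1/1.5) = 0.788.
- Closed at 12 months: d = 30.0 + 21.2 = 51.2; power = Φ(½ × 7.16 × 0.4055 − 1.96) = Φ(−0.51) = 30%.
- Cut at mid-2024: d = 45.8 + 33.7 = 79.5; power 44%.
- Cut at the end of December 2024: d = 95.8; power 51%.

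**5. Over the assumed range (deaths / power).**

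| Control one-year survival | Closed at 12 months | Cut mid-2024 | Cut end December 2024 |
|---|---|---|---|
| 50% | 87 / 47% | 124 / 62% | 142 / 68% |
| 60% | 69 / 39% | 102 / 54% | 121 / 61% |
| 70% | 51 / 30% | 80 / 44% | 96 / 51% |
| 80% | 34 / 22% | 55 / 32% | 68 / 38% |

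Comparing the two proportions at 12 months gives nearly the same power as the first column: 46%, 38%, 30% and 21%. Of the deaths observed by mid-2024, about 30-38% fall after month 12; by the end of December 2024, about 39-50%.

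**6. Sensitivity to proportional hazards.** The same design was simulated with a hazard ratio of 1.5 in year one and 1.0 afterwards. Log-rank power at 12 months / mid-2024 / end of December 2024 was about:
- S = 60%: 39 / 28 / 24%
- S = 70%: 31 / 21 / 18%
- S = 80%: 22 / 15 / 13%

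Here the longer window loses about 7-15 points.

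**The case against.** The best defence is that a one-year endpoint is a legitimate choice. The Background section bases the expected benefit on avoiding futile surgery and delayed chemotherapy, which would act early, and the patient-flow section expects liver metastases on MRI in only about 15% of the MRI arm. If the effect fades after a year, a longer window dilutes it, as step 6 shows. This stands: the gain from using all follow-up is not guaranteed. A reader might infer that closing at 12 months costs power whatever the true effect; that holds only if hazards are roughly proportional.

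Three other inferences go too far.
- **That deaths after month 12 are discarded.** They are left out of the primary endpoint, but three-year survival is planned for subsequent studies and the Kaplan-Meier plan is not truncated.
- **That every patient will have 18-36 months of follow-up at analysis.** This needs a cut at the very end of December 2024. Analysis is placed within that year with no cut-off; a cut in January 2024 would give only 6-24 months.
- **That endpoint, method and hypothesis contradict one another.** Kaplan-Meier is a standard estimator of one-year survival, and one-year survival is overall survival at one time point. The gap lies in the missing test and in the link to the hazard-ratio sizing.

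It can also be said that the low power comes mainly from reporting deaths as patients, not from the choice of endpoint. That is right, and it is why restating the power comes first in the fix.

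**Conclusion.** The point holds in this form: the 80% power does not describe the stated primary endpoint, and the primary comparison lacks a named test and a cut-off. Under a constant hazard ratio of 1.5 and control one-year survival of 50-80%, a 12-month comparison has about 47-22% power. Using all follow-up adds about 11-15 points at mid-2024 and about 17-21 points at the end of December 2024, but none of these options reaches 191 deaths or 80% power.

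That 191 is a number of deaths follows from the plan's own inputs and needs no survival assumption. The power figures do depend on the assumed control survival, exponential survival and no dropout. That a 12-month comparison falls well short of 80% holds across the whole range; that a longer window is better depends on roughly proportional hazards. Moving the primary endpoint is therefore a reasoned recommendation, while restating the power and naming the test are needed in either case.

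**What to change.** 1. Restate the power for the primary analysis in expected deaths, giving the assumed control survival and the cut-off, in place of the 80%.
2. Before any comparison by arm, specify the primary analysis as overall survival from randomisation, compared by log-rank test with a Cox hazard ratio and 95% CI, on all follow-up to one pre-set cut-off that gives every patient at least 12 months. Report the one-year Kaplan-Meier difference with 95% CI as the first secondary result.
3. State the downside: if the effect is confined to the first year, the longer window loses about 7-15 power points (control one-year survival 60-80%). If the sponsor keeps one-year survival as primary for that reason, restate the power for that endpoint and name the between-arm test.

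**Cost.** No new patients and no new data, since vital status is already to be collected for up to three years. Changing a primary endpoint is nevertheless a substantive amendment, to be carried through the registration and ethics approval that the plan foresees. The documents describe blinding only for image reading, so the timing should be tied to the first comparison by arm rather than to an unblinding step.

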Beside the salary for [name] and two research nurses mentioned above, we apply the Danish Cancer Society for expenses related to MRI scans. The departments will hold expenses for CT scans for the 50% of the patients that are expected to have more than 14 days between CT and MRI. Please see the attached budget for more details.

FUTURE PERSPECTIVES

We expect this project to substantially improve our ability to tailor the optimal treatment for each individual with pancreatic cancer. Underdiagnosis of liver metastases delays the initiation of life-prolonging chemotherapy. Thus, with proper preoperative detection of liver metastases, our project will improve both survival and quality-of-life, as patients will be spared from unnecessary major surgery. Thus, findings from our project is expected to have an immediate clinical impact. Furthermore, if MRI is non-inferior to CT with respect to tumor staging, it may replace CT in the diagnostic workup of pancreatic cancer patients.

ETHICAL CONSIDERATIONS

This project will be conducted according to the Helsinki Declaration. The project needs to be registered at the Danish Data Protection Agency in accordance with the Central Denmark Region common registration system and it also requires approval from the Central Denmark Region Ethics Committee. We will ensure that all permissions are granted when study starts. All information involving patients will be handled according to national law on personal data information. Both positive, negative, and inconclusive results will be published, and presented at scientific meetings. Results will be presented at international scientific congresses, and we will aim for publications in

high-impact journals with focus on oncology, radiology, and surgery. The study will be registered at ClinicalTrials.gov and monitored by the Good Clinical Practice Unit at Aarhus University Hospital.

REFERENCES

- Gillen S, Schuster T, Meyer Zum Buschenfelde C, Friess H, Kleeff J.
 Preoperative/neoadjuvant therapy in pancreatic cancer: a systematic review and metaanalysis of response and resection percentages. PLoS Med. 2010;7: e1000267.

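### Study I tests non-inferior MRI staging by MRI–CT agreement alone; with no reference standard for stage, a discordance cannot be attributed to either modality

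*Combined protocol and SAP*

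**What the plan says.** Under Specific study aims, hypotheses and outcomes, the aim of Study I is "To compare tumor staging of pancreatic cancer patients assessed by MRI versus upper abdominal CT". Figure 3 gives the hypothesis that "MRI is non-inferior to CT" for tumor staging, the population as the 100 intervention-arm patients, and the analysis as "Agreement assessed by" an ICC. No non-inferiority margin is given.

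Under Study design and patient flow, a CT more than 14 days older than the MRI is repeated: "a new CT will be performed to assure a valid comparator". That section sends two groups to surgery. The first is "No liver metastases on MRI (expected ~75%): Surgery as planned". The second is "Non-specific liver lesions on MRI, not seen on CT" (expected about 10%). The remaining 15% or so, with liver metastases on MRI, go to liver biopsy.

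Under Future perspectives, the result has a stated use: "if MRI is non-inferior to CT with respect to tumor staging", MRI may take the place of CT in the diagnostic workup.

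The text available for review does not name operative findings, pathology, consensus or follow-up as the standard for tumor stage. The only tissue check described is the liver biopsy, which does not verify local stage. The three-point reading scale under Analysis for metastatic lesions covers focal liver lesions only.

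**The concern.** Non-inferiority in staging is a claim about how often each modality is right. An agreement coefficient measures how often, or how closely, the two give the same answer. If MRI and CT differ on vessel involvement in a patient, the ICC falls by the same amount whether MRI or CT made the error. If they agree, they may share an error. Replacing the ICC with another agreement statistic leaves this unchanged.

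At stake is the inference drawn from Study I. Moderate agreement could hide a better MRI or a worse one, and the plan uses the answer to argue about replacing CT in the workup. Study I is not the primary end-point, which is one-year survival, so the trial's main result is not affected.

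**Working it through.** **The plan's own figures.** No sample size or precision is stated for Study I. The only calculation, under Power calculations and feasibility, gives 191 for a hazard ratio of 1.5, alpha 0.05 and 80% power. It reproduces as 4 × (1.960 + 0.8416)² / (ln 1.5)² = 191. It concerns survival in Study III and says nothing about staging. (The formula counts deaths while the plan says patients; that is a separate matter.)

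**Patients with operative findings.** The expected shares sent to surgery give 100 × (0.75 + 0.10) = 85. With the plan's 5% dropout, 95 × 0.85 = 80.75, about 81. Fewer will have a full pathological stage, because a patient found unresectable at exploration is operated but not resected. I take 70 as an assumed lower case.

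**What agreement can and cannot show.** Take 85 patients and an assumed two-category stage:

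| | MRI high | MRI low |
|---|---|---|
| CT high | 30 | 5 |
| CT low | 10 | 40 |

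- Raw agreement = (30 + 40)/85 = 82.4%.
- ICC (two-way, absolute agreement, k = 2 modalities, n = 85) = (MSR − MSE) / [MSR + (k − 1)MSE + k(MSC − MSE)/n]. With between-patient MSR = 0.4097, between-modality MSC = 0.1471 and residual MSE = 0.0875, this is 0.3221/0.4986 = 0.65.
- If MRI is always right: MRI 100%, CT 82.4%, difference (MRI − CT) +17.6 points.
- If CT is always right: MRI 82.4%, CT 100%, difference −17.6 points.

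The planned statistic is 0.65 in both cases.

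**The bound from raw discordance.** The accuracy difference equals P(MRI right, CT wrong) − P(CT right, MRI wrong). Both events require the modalities to differ, so the absolute difference cannot exceed the proportion discordant. At 95% raw agreement it is at most 5 points, whatever the truth. At 82.4% it is anywhere within ±17.6 points. The ICC does not supply this bound, because its value also depends on how widely stages are spread in the sample.

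**Precision with a reference standard.** Let ψ be the proportion of patients in whom exactly one modality is right. The documents do not give ψ, so the range is assumed. At equal accuracy, the 95% half-width is 1.96 × √(ψ/n), and the margin testable with 80% power at one-sided 0.025 is (1.96 + 0.8416) × √(ψ/n). In percentage points:

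| ψ | Half-width, n = 85 | Half-width, n = 70 | Margin, n = 85 | Margin, n = 70 |
|---|---|---|---|---|
| 10% | 6.7 | 7.4 | 9.6 | 10.6 |
| 15% | 8.2 | 9.1 | 11.8 | 13.0 |
| 20% | 9.5 | 10.5 | 13.6 | 15.0 |
| 30% | 11.6 | 12.8 | 16.6 | 18.3 |

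At n = 81 the half-widths run from 1.96 × √(0.10/81) = 6.9 to 1.96 × √(0.30/81) = 11.9 points.

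**The case against.** **CT is only a comparator.** A reader might infer that the plan treats CT as the truth, so that each MRI correction of a CT error counts against MRI. The documents do not support that. They call CT a comparator, and an agreement statistic treats both modalities alike. Discordance is unattributed, not charged to MRI.

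**High agreement could be enough.** It is also tempting to say that Study I can never answer its question. That is too strong: with very high raw agreement and a margin, the bound above could support non-inferiority without pathology. This part of the objection stands. But the plan names neither raw agreement nor a margin, and it cannot count on discordance being that small.

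**The remedy has its own selection.** This stands and must be stated. Every patient is CT-resectable at entry. On resectability the qualifying CT is therefore constant, and CT over-staging to unresectable cannot be seen. A paired comparison here is conditional on that CT result.

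**Surgery may depend on the MRI.** The three written branches mention only liver findings, so one might infer that patients are operated, and stage thereby verified, regardless of what MRI shows locally. This is not established. The same section says that treatment is decided from the MRI, and Figure 2, whose legend mentions the multidisciplinary conference, could not be seen.

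**The reference may be thinner than it looks.** It would be wrong to read 85 as the number with a reference stage. It is the expected number sent to surgery and so an upper figure. Routine pathology is an assumption, since the available text does not mention it.

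**Conclusion.** The point holds in this form: Study I states a non-inferiority hypothesis about staging, plans only an MRI–CT ICC, and names no reference standard in the text available. Unless raw discordance is very small, that analysis cannot show non-inferior staging accuracy, and so cannot carry the suggestion that MRI might replace CT. This is more than missing detail, because carrying out the plan exactly as written would not test its hypothesis.

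A usable reference is within reach, but it is limited. Operative findings would exist for at most about 85 patients, and the 95% half-width would be roughly ±6.7 to ±11.6 points, widening to ±7.4 to ±12.8 if only 70 are usable. These figures assume equal accuracy, 10–30% of patients with exactly one modality right, and that resected specimens are routinely examined. With such precision only a fairly wide margin could be tested. Even the corrected analysis speaks to CT-resectable, operated patients and not to an unselected diagnostic population.

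**What to change.** - Make the test of the Study I hypothesis a paired comparison in operated MRI-arm patients. Classify the MRI stage and the CT stage (local extent, vessel involvement) as correct, over-staged or under-staged against operative findings and, where resected, pathology. Report the paired difference in proportion correct with a 95% confidence interval (McNemar-type).
- Fix the stage categories, the reference definition, the margin, and which CT counts when it was repeated, before the data are examined.
- Keep MRI–CT agreement for all 100 patients as descriptive, and report raw agreement beside the ICC.
- List non-operated patients, and any whose surgery was changed because of MRI, separately as unverified.
- State that the result applies to CT-resectable, operated patients, and that CT over-staging to unresectable cannot be observed. Word the replacement claim accordingly.

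The cost is plan wording and abstraction of operative and pathology reports for up to about 85 patients. Study I already needs a stage from each modality, but the only reading scale described is for liver lesions, so local stage must be recorded in a standard form on both. The downsides are a smaller N and a selected population.
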